2.3 Correlative Research

2.31 To conduct correlative studies for further understanding of the mechanism of antitumor activity of ibrutinib in eradication of the MRD.

2.32 Determine the impact of ibrutinib on depression and anxiety symptoms to better understand toxicity profile of ibrutinib maintenance.

2.33 Determine impact of social support or lack thereof on mood symptoms in CLL patients receiving maintenance treatment.

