4.0 Test Schedule

All visits \pm 4 days unless otherwise stated.

| Tests & Procedures | Active Monitoring Phase | | | | | |
|---|----------------------------|-----------------|---------------|---|----------------------------|-------------|
| | Days Prior to Registration | \leq 14 days | Cycle 1 (Pre) | Prior to subsequent Cycles 2-36 | Study Drug Discontinuation | Observation |
| | | | | 3-4 weeks from the last day of the last cycle | | |
| Complete medical history (including prior treatment regimen) | X | | | | | |
| Adverse event assessment | X | | | X | X | X |
| Physical exam, including weight and vital signs, and PS ¹ | | X | X | X ²⁰ | X | X |
| Clinical Response assessment (Tumor measurement by physical exam) ^{2, 3} | | X | | X | X | X |
| CT scans (Chest, Abdomen, Pelvis) ⁴ | X | | | | X | |
| EKG/ECHO ⁵ | X | | | | | |
| CBC with differential ⁶ | | X | X | X | X | X |
| Chemistry group (SGOT [AST], SGPT [ALT], serum creatinine, total bilirubin, LDH, uric acid, phosphorus, alkaline phosphate, serum electrolytes) ⁶ | | X | X | X | X | X |
| Direct bilirubin ¹⁵ | | X | | | | |
| Quantitative Immunoglobulins | X | | | X ⁷ | X | |
| Quantitative T & B cells, peripheral blood | | X | | X ¹⁷ | | |
| Minimal residual disease assessment ⁸ | X | | | X | X | X |
| Flow Cytometry-CLL Panel ⁹ | X | | | | | |
| Bone marrow biopsy and/or aspirate ¹⁰ | X | | | X | X | X |
| CLL FISH Panel ¹¹ , | X | | | | | |
| Zap 70, CD38, IgHV ¹² | X | | | | | |
| Beta 2 microglobulin ¹² | X | | | | | |
| Research blood sample collection ^{13, R} | | X | | X | X | X |
| Research bone marrow aspirate collection ^{14, R} | X | | | X | X | X |
| Mandatory DNA sample which can be collected from any one of the 3 sources (buccal swab, skin biopsy or myeloid cells from bone marrow) as noted in Section 17.0 | | X ¹⁸ | | | | |
| Urine Pregnancy test | | X ¹⁶ | | | | |
| PHQ-8; GAD; Living Situation; MOS-SSS-4 Question; QOL | | X | | X ¹⁹ | | |

1. During the first 2 cycles of treatment, patients will have a focused clinical examination weekly, as necessary, for the monitoring of tumor lysis syndrome (TLS). This can be done in collaboration with local MD/referring physician.

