14. Bone marrow aspirate (optional) for correlative studies, see Section 14.0. Samples will be collected only if bone marrow biopsy or aspirate is done as part of routine clinical care of the patient (as outlined in footnote 10) or as part of MRD assessment (as noted in footnote 8).
15. Only for patients with Gilbert's syndrome and the total bilirubin >1.5 mg/dL.
16. For women of childbearing potential only. Must be done ≤ 7 days prior to registration.
17. Should be performed after 3 cycles, 6 cycles, 12 cycles, and at time of relapse.
18. Buccal swab may be collected any time prior to starting treatment. Skin biopsy is only required if DNA cannot be obtained from the buccal swab. Alternate source could be myeloid cells in the marrow (in cases where bone marrow is obtained). This will be at the discretion of the treating physician in consultation with the PI.

19. PHQ-8, GAD-7, Living situation, MOS-SSS-4 Question, and Linear Analogue Self-Assessment: Prior to cycle 4, prior to cycle 7, prior to cycle 13, at time of relapse and thereafter every 3 months x4.
20. After the first 6 cycles, clinical evaluation and blood tests can be obtained per test schedule and mailed/faxed to Mayo Clinic and patient can return at least every 3 cycles for follow up to Mayo. Patient may be seen more frequently, if clinically necessary. NOTE: All forms, including AEs, will need to be filled out every 28 days.

R. Research funded.

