7.0 Protocol Treatment

7.1 Treatment Schedule

| Agent | Dose | Route | Days | Max. No. of cycles |
|-----------|-----------|-------|------|--------------------|
| Ibrutinib | 420 mg QD | Oral | 1-28 | 36 |

Cycle length = 28 days

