7.11 Ibrutinib

- 420mg PO QD will begin on day one of cycle #1.
- Four weeks will constitute 1 treatment cycle.
- Patients will be evaluated for MRD status every 3 cycles (as discussed previously in Section 4.0, footnote 8, see detailed MRD section 11.4).
- A maximum of 36 cycles of maintenance cycles will be given.
- Treatment will be discontinued if (a) patients develop unacceptable side effects, (b) if patients develop disease progression while on ibrutinib maintenance (recommended to be confirmed on two independent occasions at least 2 week apart and consistent with the IWCLL guidelines, see Section 11.0), (c) if patients have completed the 36 cycles on maintenance therapy, (d) if the patient is removed from the study by the treating physician due to concern of overall wellbeing and in the best interest of the patient, (e) patients who have residual disease at the end of 36 cycles will continue to event monitoring

7.2 Treatment by Local Medical Doctor (LMD): If patient is tolerating therapy without excessive toxicity at a stable dose level after 1 cycle (can be confirmed through telecommunication and does not need to be physically evaluated at Mayo Clinic) of treatment the patient may be seen by their primary physician (if outside of Mayo Clinic). Results would need to be returned to Mayo Clinic. Patient would need to return to Mayo Clinic every 3 cycles for follow-up at Mayo Clinic.

7.3 After the first 6 months, clinical evaluation and blood tests can be obtained per test schedule and mailed/faxed to Mayo Clinic and patient can return at least every 3 cycles for follow up to Mayo (patient does not need to be seen every cycle). Patient may be seen more frequently, as clinically necessary. All unused study drug must be returned, and all study drug must be accounted for. A 3-month supply of study drug may be provided at each cycle.

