9.8 Psychosocial Assessment: Assessing psychosocial factor is important in cancer patients. The Patient Health Questionnaire 8 (PHQ-8, which is a version of the PHQ-9) will be used to screen for depression symptoms. This is a validated tool in cancer patients when scored as a continuous measure with a cutoff score of 8 or higher. Item 9 on this scale inquires about “thoughts that you would be better off dead or of hurting yourself in some way”. Cancer patients are likely to consider the prospect of death while thinking about their prognosis. This makes this question more ambiguous in this population. Kroenke et al have reported that using PHQ-8 is desirable in conditions where data is collected in settings where real time further follow up questions about response to item 9 on PHQ-9 is not feasible. After comparing the data from PHQ-9 studies they concluded that PHQ-8 is an acceptable alternative to PHQ-9. When using cut off score of 10 or higher, PHQ-8 has 99% sensitivity, 92% specificity and 57% positive predictive value (2) (See appendix VIII)

The GAD-7 (Generalized Anxiety Disorder) self-reported scale will be used to assess anxiety symptoms (See appendix IX).

Subjects will be asked about their living situations by asking:

What best describes your living situation:

- I live with a partner/spouse/family/friends
- I live alone
- I live in a nursing home, hospital, or other long-term care home
- Other

Social support will be assessed by using 4 questions from the Medical Outcomes Study: Social Support Survey (MOS-SSS) (See appendix X).

These will be collected at baseline at the time of study enrollment and will be repeated quarterly.

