13.0 Treatment/Follow-up Decision at Evaluation of Patient

- 13.1 If the patient develops PD at any time during active treatment they will go to event monitoring. If the patient develops unacceptable adverse events, if the treating physician feels it is in the patient's best interest, or if the patient refuses all further study participation, study treatment will be discontinued, and the patient will go directly to event monitoring. Patients will then be followed in event monitoring per Section 18.0.
- 13.2 Patients not progressing on active treatment will continue treatment per protocol up to a maximum of 36 cycles. After the completion of 36 cycles, the patient will go to observation (maximum duration of observation 2 years). After completing observation, patients will enter event monitoring. NOTE: Patients who have residual disease at the end of 36 cycles will continue to event monitoring.
- 13.3 A patient is deemed ineligible if after registration, it is determined that at the time of registration, the patient did not satisfy each and every eligibility criteria for study entry. The patient may continue treatment off-protocol at the discretion of the physician as long as there are no safety concerns and as long as the patient was properly registered. The patient will go directly to the event-monitoring phase of the study (or off study, if applicable).
 - If the patient received treatment, all data up until the point of confirmation of ineligibility must be submitted. Event monitoring will be required per Section 18.0 of the protocol.
 - If the patient never received treatment, on-study material and the End of Active Treatment/Cancel Notification Form must be submitted. No further data submission is necessary.

Note: Due to the nature of the disease, if the patient is diagnosed with DLBCL within the first cycle of treatment, it will be assumed that the DLBCL was present at registration. The patient will be deemed ineligible per Sec 3.27.

- 13.4 A patient is deemed *cancel* if he/she is removed from the study for any reason before any study treatment is given. On-study material and the End of Active Treatment/Cancel Notification Form must be submitted. No further data submission is necessary.

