18.0 Records and Data Collection Procedures

18.1 Submission Timetable

Initial Material(s)

| | Active-Monitoring Phase (Compliance with Test Schedule Section 4.0) |
|--|---|
| CRF | |
| On-Study | |
| Adverse Event - Baseline | |
| Measurement - Baseline | |
| Research Blood Submission - Baseline (See section 14.0) | |
| Research Bone Marrow Aspirate Submission - Baseline (See section 14.0) | |
| Bone Marrow Biopsy | |
| FISH Results - Baseline | |
| Quantitative Flow Cytometry | |
| Pre-induction and pre-registration immunophenotyping/pre-registration MRD reports including CD38 and ZAP-70 ^{1,2} | |
| IgVH Mutation Analysis Report ¹ | |
| Other Laboratory Results | |
| CLL FISH Report ¹ | |
| Bone Marrow Biopsy Report ¹ | |
| CT Scan Report ¹ | |
| Research Tissue Submission - Baseline | |
| Psychology and QOL Assessments - Baseline | |
| End of Active Treatment/Cancel Notification | Submit \leq 2 weeks after registration if withdrawal/refusal occurs prior to beginning protocol therapy |

1. Submit copy of the report, Attention: QAS for MC1481, [contact].
2. For patients who previously had full flow immunophenotyping performed and at pre-study workup had limited repeat flow immunophenotyping, submit a copy of both reports.

Test Schedule Material(s)

| CRF | Active-Monitoring Phase (Compliance with Test Schedule Section 4.0) | | |
|---|--|------------------------|----------------|
| | At each evaluation during treatment | At end of treatment | Observation |
| Evaluation/Treatment | X ² | X | |
| Evaluation/Observation | | | X ¹ |
| Nadir/Adverse Event | X | X | X |
| Measurement | X | X | X |
| Quantitative Flow Cytometry | X ⁴ | X | X |
| Research Blood Submission | X ⁴ (see Section 14.0) | X | |
| Research Bone Marrow Aspirate Submission | X ⁴ (see Section 14.0) | X | |
| Bone Marrow Biopsy | X ⁴ | X ⁴ | X ⁴ |
| Other Laboratory Results | X | X | X |
| Immunophenotyping/MRD Report ³ | X ⁴ | X ⁴ | |
| Bone Marrow Biopsy Report ³ | X ⁴ | X ⁴ | |
| CT Scan Report ³ | X ⁴ | X ⁴ | |
| Psychology and QOL Assessments | X ⁴ | X ⁴ | |
| End of Active Treatment/Cancel Notification | | X | |
| ADR/AER | At each occurrence (see Section 10.0) | | |

1. Complete at each evaluation during Observation (see Section 4.0).
2. Complete at each evaluation during Active Treatment (see Section 4.0).
3. Submit copy of the report, Attention: QAS for MC1481, [contact].
4. Complete when required per the test schedule.

Follow-up Material(s)

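### Section 9.8 collects the mood and social-support questionnaires quarterly, but the test schedule gives 3 on-treatment assessments (about 7 on another reading) instead of 11, leaving the last third to two thirds of 36 cycles without one

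*Combined protocol and SAP*

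**What the plan says.** Four parts of the protocol bear on when the questionnaires are given.

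- **Section 9.8 (Psychosocial Assessment)** covers the PHQ-8, the GAD-7, living situation and four MOS-SSS items: "These will be collected at baseline at the time of study enrollment and will be repeated quarterly". It gives no end date and no relapse condition.
- **Section 4.0 (Test Schedule)** has one row for them, "PHQ-8; GAD; Living Situation; MOS-SSS-4 Question; QOL", marked before registration and under the column for cycles 2 to 36. There is no mark under Study Drug Discontinuation or Observation. Footnote 19, attached to the on-treatment mark, adds the linear analogue scale and sets the times: "Prior to cycle 4, prior to cycle 7, prior to cycle 13, at time of relapse and thereafter every 3 months x4".
- **Section 18.1 (Submission Timetable)** lists the psychology and quality-of-life forms both during treatment and at end of treatment. Each entry carries note 4: "Complete when required per the test schedule".
- **Section 2.3** states what the data are for. Goal 2.32 is: "Determine the impact of ibrutinib on depression and anxiety symptoms to better understand toxicity profile of ibrutinib maintenance". Goal 2.33 concerns social support and mood in patients on maintenance treatment. Section 16.332 makes the mood analyses exploratory and descriptive.

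On treatment length, Section 7.11 states: "A maximum of 36 cycles of maintenance cycles will be given". Section 7.1 states: "Cycle length = 28 days".

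**The concern.** Sections 9.8 and 4.0 prescribe different schedules for the same instruments. They differ even in the first year, because footnote 19 skips the visit before cycle 10. Note 4 of Section 18.1 defers to the test schedule, so the sparser schedule decides which forms are due.

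The word *thereafter* in footnote 19 has no clear anchor. It can follow relapse or the cycle 13 visit, and the two readings give very different coverage.

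What is at stake is the use of the scores for goals 2.32 and 2.33. Both concern patients on maintenance, which can last 36 cycles. If most scheduled scores fall in the first 12 cycles, the data say little about mood later on the drug. If the only later scores come from relapsed patients, a late change mixes relapse, stopping ibrutinib and any next therapy with a drug effect. With two schedules in force, an analyst also cannot tell a missed form from one that was never due.

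**Working it through.** The plan states no figure for questionnaire coverage, so there is nothing to reproduce. The check is schedule arithmetic.

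**Inputs.** Maximum 36 cycles (Section 7.11); 28-day cycles (Section 7.1); quarterly repeats (Section 9.8); assessments before cycles 4, 7 and 13, then the relapse clause (footnote 19).

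**Length of treatment.** 36 × 28 = 1008 days.

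**Assessments under Section 9.8.**
- Every 3 cycles means before cycles 4, 7, 10, ..., 34: (34 − 4)/3 + 1 = 11.
- By calendar quarter: 1008/91.3 = 11.04, so again 11.
- Seven of the 11 fall after the cycle 13 visit (before cycles 16, 19, 22, 25, 28, 31 and 34).

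**Footnote 19, reading A: the three-monthly run starts at relapse.**
- On-treatment assessments without relapse: 3 (before cycles 4, 7 and 13).
- Shortfall: 11 − 3 = 8, namely the seven after cycle 13 plus the one before cycle 10.
- Last assessment: after 12 × 28 = 336 days.
- Uncovered: 1008 − 336 = 672 days, or 24 cycles; 672/1008 = 67%.
- Gap between the cycle 7 and cycle 13 visits: 6 × 28 = 168 days, against 84 days at 3-cycle spacing.

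**Footnote 19, reading B: the run starts at cycle 13 for everyone.**
- On-treatment assessments: 3 + 4 = 7 of 11.
- At 84-day spacing the last falls after 336 + 4 × 84 = 672 days (before cycle 25). Uncovered: 336/1008 = 33%.
- At calendar quarters it falls after 336 + 4 × 91.3 = 701 days. Uncovered: 307/1008 = 30%.

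| | Section 9.8 | Reading A | Reading B |
|---|---|---|---|
| On-treatment assessments after baseline, no relapse | 11 | 3 | 7 |
| Treatment after the last assessment | under one quarter | 67% | 30–33% |

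**Which reading is more natural.** In the sentence, *thereafter* directly follows the relapse time point. Footnotes 13 (research blood) and 17 (T and B cells) have the same shape: early visits up to cycle 13 or 12 completed cycles, then relapse. Both favour reading A.

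**Where post-relapse forms would go.** Under reading A a relapsed patient is due up to 1 + 4 = 5 further assessments. Section 13.1 says: "If the patient develops PD at any time during active treatment they will go to event monitoring". The event-monitoring table in Section 18.1 lists only the Event Monitoring form, so these questionnaires have no stated collection route.

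**End of treatment.** Section 18.1 lists the forms there, but only as the test schedule requires, and the test schedule has no mark at discontinuation. As written, that entry is never triggered.

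**The case against.** The best case against the point is that the footnote is ambiguous and the consequences are small.

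*Reading B has support.* The footnote mark sits in the on-treatment column, reading B lies closer to the quarterly rule, and reading A sends questionnaires into a phase with no form for them. Footnotes 13 and 17 also lack any three-monthly run, so they match only the list of visits. This stands: the 67% figure and the claim about relapsed patients are conditional on reading A. The contradiction with Section 9.8 is not, since reading B still leaves about a third of treatment uncovered.

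*The sparse schedule may be deliberate.* Cycles 4, 7 and 13 plus relapse match the research blood sampling, and nothing gives Section 9.8 precedence. This stands too, so correcting Section 9.8 is a legitimate alternative.

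*Section 18.1 lists the forms at end of treatment.* That suggests an assessment was intended there, but note 4 returns the question to a schedule that shows none. The blank cells should be confirmed in the printed table.

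*Footnote 20 asks for all forms every 28 days.* This does not close the gap. The questionnaire entries defer specifically to the test schedule, and footnote 20 read literally would add a third frequency.

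*A reader might infer that mood goes unobserved for two thirds of treatment and that a safety screen has lapsed.* The documents do not support this. Adverse events are assessed before every cycle, and Section 10.62 submits related grade 2 events and all grade 3 and 4 events, so a clinically evident mood reaction has a reporting route. Section 9.8 speaks of screening but ties no alert or action to any score. What is missing is scheduled questionnaire scores.

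*The study is single-arm with 32 evaluable patients.* Even 11 assessments could not separate a drug effect from time or disease. This is true, and it limits what the fix can achieve. A descriptive account of mood on maintenance still needs scores taken during maintenance.

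**Conclusion.** The point holds as an internal contradiction with a moderate effect on two exploratory goals. Sections 9.8, 4.0 (footnote 19) and 18.1 cannot all be followed as written. A patient who completes 36 cycles without relapse has 3 of the 11 quarterly assessments and no scheduled scores for 24 cycles (67%) on the more natural reading, or about 7 of 11 with 30% to 33% uncovered on the other. Only on the first reading do all later scores come from relapsed patients.

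These figures assume the full 36 cycles without relapse and without long interruptions. Quarterly is taken as every 3 cycles; calendar quarters give the same count of 11.

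The effect stops at goals 2.32 and 2.33. The primary endpoint, the secondary endpoints, the sample size and the decision rule do not use these data. The change should be made, but the trial's main conclusion does not depend on it.

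**What to change.** Reconcile Sections 9.8, 4.0 (footnote 19) and 18.1:

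1. In footnote 19, give the booklet (PHQ-8, GAD-7, living situation, MOS-SSS items and linear analogue scale) before cycles 4, 7, 10, ..., 34. Patients already return at least every 3 cycles, and MRD is tested on the same rhythm.
2. Mark the booklet at the Study Drug Discontinuation visit in the test schedule, as Section 18.1 implies.
3. State what the closing three-monthly run follows. If post-relapse assessments are kept, add the form to the event-monitoring table.
4. In Section 16.332, summarise post-relapse assessments separately from on-treatment ones.

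The cost is an amendment to a few lines, up to 8 more short booklets per patient at existing visits, and one at discontinuation.

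If the sparse schedule is intended, correct Section 9.8 to match it, still define the closing run, and limit conclusions on goals 2.32 and 2.33 to the first 12 cycles. That adds no booklets but gives up any description of mood later in maintenance.

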5.0 Grouping Factor: None.**6.0 Registration Procedures**

6.1 To register a patient, access the Mayo Clinic Cancer Center (MCCC) web page and enter the registration/randomization application. The registration/randomization application is available 24 hours a day, 7 days a week. Back up and/or system support contact information is available on the Web site. If unable to access the Web site, call the MCCC Registration Office at [contact] between the hours of 8 a.m. and 4:30 p.m. Central Time (Monday through Friday).

The instructions for the registration/randomization application are available on the MCCC web page (<http://hsrwww.mayo.edu/ccs/training>) and detail the process for completing and confirming patient registration. Prior to initiation of protocol treatment, this process must be completed in its entirety and a MCCC subject ID number must be available as noted in the instructions. It is the responsibility of the individual and institution registering the patient to confirm the process has been successfully completed prior to release of the study agent. Patient registration via the registration/randomization application can be confirmed in any of the following ways:

- Contact the MCCC Registration Office [contact]. If the patient was fully registered, the MCCC Registration Office staff can access the information from the centralized database and confirm the registration.
- Refer to "Instructions for Remote Registration" in section "Finding/Displaying Information about A Registered Subject."

6.2 Registration to the Correlative Research

Mandatory:

A mandatory correlative research component is part of this study, the patient will be automatically registered onto this component (see Sections 3.13, 4.0, 14.0 and 17.0).

6.3 Prior to accepting the registration, registration/randomization application will verify the following:

- IRB approval at the registering institution
- Patient eligibility
- Existence of a signed consent form
- Existence of a signed authorization for use and disclosure of protected health information

6.4 Documentation of IRB approval must be on file in the Registration Office before an investigator may register any patients.

In addition to submitting initial IRB approval documents, ongoing IRB approval documentation must be on file (no less than annually) at the Registration Office ([contact]). If the necessary documentation is not submitted in advance of attempting patient registration, the registration will not be accepted, and the patient may not be enrolled in the protocol until the situation is resolved.

When the study has been permanently closed to patient enrollment, submission of annual IRB approvals to the Registration Office is no longer necessary.

- 6.5 At the time of registration, the following will be recorded:
 - Patient has/has not given permission to store and use his/her sample(s) for future research of CLL at Mayo Clinic.
 - Patient has/has not given permission to store and use his/her sample(s) for future research to learn, prevent, or treat other health problems.
 - Patient has/has not given permission for MCCC to give his/her sample(s) to researchers at other institutions.
- 6.6 Treatment on this protocol must commence at Mayo Clinic under the supervision of a medical oncologist or hematologist.
- 6.7 Treatment cannot begin prior to registration and must begin \leq 14 days after registration.
- 6.8 Pretreatment tests/procedures (see Section 4.0) must be completed within the guidelines specified on the test schedule.
- 6.9 All required baseline symptoms (see Section 10.6) must be documented and graded.
- 6.9a Study drug is available on site.
- 6.9b **Patient Questionnaire booklets**
Patient questionnaire booklets are available on site. Copies are not acceptable for these submissions. Booklets should be ordered using the Patient Questionnaire Order Form.

